5.3.4 Multiple Measurements within Visit Windows

If multiple non-missing continuous measurements exist in an analysis window, the measurements will be selected based on the following rules if a single value is needed:

- For Baseline visit, the assessment closest to and prior to the time of the first dose of open-label study drug, whether scheduled or unscheduled, will be used as the baseline value. If multiple measurements occur on the same day at the same time or the time is not available, the one with later nominal visit (scheduled visits take precedence over unscheduled visit) will be selected.
- For post-baseline visits, the assessment closest to the target study day will be selected for the by-visit analyses. In these analyses, if two assessments are equidistant from the target day then the chronologically last assessment will be used. If multiple assessments have the same date/time, the one with later nominal visit (scheduled visits take precedence over unscheduled visit) will be selected.

If multiple non-missing categorical measurements exist in an analysis window, the measurements will be selected based on the following rules if a single value is needed:

- For Baseline visit, the assessment closest to and prior to the time of the first dose of open-label study drug, whether scheduled or unscheduled, will be used as the baseline value. If multiple measurements occur on the same day at the same time or the time is not available, the value with the lowest severity will be selected.
- For post-baseline visits, the assessment closest to the target study day will be selected for the by-visit analyses. In these analyses, if two assessments are equidistant from the target day then the chronologically last assessment will be used. Exceptions may be made for incomplete assessments, in which case, more complete assessments may be given priority. If multiple measurements occur on the same day, the value with the highest severity will be selected.

For safety analysis where the most extreme values should be selected (e.g. overall post-baseline minimum, overall post-baseline maximum, and potentially clinically important values), all non-missing post-baseline values should be considered, regardless of whether the value is selected for the by-visit summaries. All results will be presented in data listings.

When ECG is collected in triplicate, the average of the triplicate will be considered as one assessment for the analyses.

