where possible. For all visits that are conducted remotely, the Investigator **must** contact the Medical Monitor for approval of the plan. Sites must keep a log to identify details of all visits that are administered remotely. Provided that the subject is physically in the clinic, and accompanied by a relative, all caregiver-rated assessments may be provided remotely.

- d Consent from the subject, parent/LAR, and caregiver (if different from the parent/LAR), for the present study must be obtained for entry into the present study prior to the final procedures being performed at the end of treatment (EOT) visit in the antecedent double-blind study. Data from the EOT/ET visit procedures of the antecedent double-blind study will be carried over as baseline information in the present study, as applicable
- e All assessments must be completed and subject must meet required eligibility criteria before being enrolled.
- f 12-lead ECGs should be performed in sequential triplicate. Electrocardiograms should be performed before blood sampling or at least 30 minutes after blood sampling. The subject must rest in a sitting or supine position for 5 minutes before the ECG is obtained. One repeat set of triplicate ECGs is allowed at Baseline.
- g Mild sedation is allowed exceptionally for ECGs and blood draws during the study (e.g., alprazolam at a pediatric-appropriate dose per age, and the *lowest dose* deemed necessary by the Investigator) just in cases when the subject's agitation/anxiety does not allow a safe and accurate measurement and the Investigator, with agreement from the caregiver, considers it safe and appropriate for the subject.
- h For female subjects of childbearing potential, a urine pregnancy dipstick test will be completed at all scheduled and unscheduled visits. If positive, the result will be confirmed with a serum pregnancy test.
- i Relative to baseline status in the antecedent double-blind study.
- j The subject and their parent/LAR will be provided instructions for the subject's first dose of study drug on the day after the Baseline visit.
- k Study drug may be dispensed to the subject at unscheduled visits if needed.
- l If visit is remote, accountability will be assessed verbally with the caregiver, and verified at the next clinic visit.
- m The involvement of experienced personnel in the conduction of routine procedures such as blood drawing and ECG recording in this population is strongly recommended.

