14.4 Electrocardiogram (ECG)

12-lead electrocardiograms are performed at Baseline, Week 2, Week 6, Week 12, Week 20, Week 28, Week 36, Week 44, and Week 52 visits.

All tracings will be evaluated by a central reading laboratory. At the Baseline visit, the machine-read results will also be recorded. All data, including the machine-read Baseline results, will be listed. ECG data summaries will be performed using the centrally evaluated data.

Observed values of ECG variables (heart rate, PR interval, RR interval, QRS interval, QT interval, and QTc intervals) and the changes from baseline at each assessment timepoint will be summarized. QTc intervals include QTcB (Bazett's formula) and QTcF (Fridericia's formula).

QTcF will also be categorized into the following categories (msec) and the number and percentage of subjects in each category will be summarized at each visit and for the overall post-baseline maximum:

- Observed: ≤450, 451 to 480, 481 to 500, and >500
- Change from Baseline: ≤10, 11 to 30, 31 to 60, and >60

For cardiologist's interpretations, the number and percentage of subjects with ECG results that are determined as normal or abnormal will be summarized at scheduled visits. The overall post-baseline worst interpretation will also be summarized (i.e. if a subject has one or more post-baseline ECG results that is/are considered as abnormal, this subject will be counted in the abnormal category). Cardiologist's interpretations will also be summarized in a shift table to determine the number and percentage of subjects with ECG results classified as normal or abnormal at scheduled post-baseline visits relative to the same classification at the Baseline visit. The shifts from Baseline to overall post-baseline worst interpretation will also be presented. For the by-visit shift summary, the denominator is the number of subjects with non-missing cardiologist's interpretation at Baseline and the given visit for the given cohort. For the summaries of shift from Baseline to the overall post-baseline worst interpretation, the denominator is the number of subjects with non-missing Baseline and at least one post-baseline cardiologist's interpretation for the given cohort.

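### The same-day selection rule for categorical values differs between Baseline and later visits, so the by-visit ECG normal/abnormal shift table can show net worsening when nothing has changed

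*SAP*

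**What the plan says.** SAP 5.3.4 has separate rules for continuous and categorical measurements.

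- **Categorical, Baseline.** The value used is "the assessment closest to and prior to the time of the first dose of open-label study drug, whether scheduled or unscheduled". If same-day values share a time or have no time, "the value with the lowest severity will be selected".
- **Categorical, post-baseline.** The assessment nearest the target day is taken, and the later one if two are equally near. For several values on one day: "If multiple measurements occur on the same day, the value with the highest severity will be selected". This sentence carries no condition on time.
- **Continuous.** The tie-break is the same at Baseline and afterwards: the later nominal visit, with scheduled visits ahead of unscheduled ones.
- **Triplicate ECGs.** The section closes with: "When ECG is collected in triplicate, the average of the triplicate will be considered as one assessment for the analyses".

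Protocol Table S-1, footnote f, says "12-lead ECGs should be performed in sequential triplicate". The schedule has ECGs at Baseline and eight later visits, and one repeat set is allowed at Baseline. SAP 14.4 adds: "All tracings will be evaluated by a central reading laboratory". It then specifies: "Cardiologist's interpretations will also be summarized in a shift table to determine the number and percentage of subjects with ECG results classified as normal or", the other class being abnormal, for each later visit against Baseline. A second shift table runs from Baseline to the worst post-baseline interpretation.

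**The concern.** A shift table is informative only if both margins are measured in the same way. Here the Baseline margin uses the last pre-dose value (or the mildest), and the visit margin uses the worst value of the day. If a subject's same-day readings disagree, that difference alone can move the subject from normal to abnormal.

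Several tracings on one day are the design for ECGs, not an exception. The averaging sentence does not settle how they are handled in this table: an average exists for QTcF, but not for a normal/abnormal reading. A programmer must either invent a reduction rule or fall back on the categorical rule, which is asymmetric.

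ECG is one of the safety measures listed under the primary objective (Protocol 2.1.1). The study is single-arm and descriptive, so these tables are themselves the evidence. A reader could not separate shifts created by the rule from shifts caused by the drug.

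**Working it through.** **Direction.** This needs no model. Within any same-day set, highest severity ≥ last value ≥ lowest severity. If a subject's tendency to abnormal readings is unchanged, the expected net shift (normal-to-abnormal minus abnormal-to-normal) is P(abnormal under the visit rule) − P(abnormal under the Baseline rule). That is zero if same-day readings never disagree, and positive otherwise.

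**Size: inputs.** The plan states no figure to reproduce.

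- Tracings per visit: 3 (Protocol Table S-1, footnote f).
- Planned subjects: about 193 (SAP 3.5), used only to turn percentages into counts.
- Assumed, because the documents give nothing: mean abnormal rate per tracing p = 5% to 10%; within-subject correlation ρ = 0.3 to 0.6; a subject's propensity q is Beta-distributed and the same at Baseline and at the visit; readings are independent given q; one interpretation is recorded per tracing; Baseline tracings are timed, so the last one is used.

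**Formulas.** Let s = (1 − ρ)/ρ and M(k) = E[(1 − q)^k] = the product over j = 0 to k − 1 of [1 − ps/(s + j)].

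- SAP rule (last at Baseline, highest at the visit): normal-to-abnormal = E[(1 − q){1 − (1 − q)³}] = M(1) − M(4); abnormal-to-normal = E[q(1 − q)³] = M(3) − M(4).
- Highest severity at both times: M(3) − M(6) in each direction.

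**Numbers at the two ends of the range.**

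| | p = 5%, ρ = 0.6 | p = 10%, ρ = 0.3 |
|---|---|---|
| M(1), M(3), M(4), M(6) | 0.9500, 0.9194, 0.9110, 0.8992 | 0.9000, 0.7919, 0.7573, 0.7062 |
| SAP rule, normal-to-abnormal | 3.9% | 14.3% |
| SAP rule, abnormal-to-normal | 0.8% | 3.5% |
| Net, 1 − M(3) − p | 3.1%, about 6 of 193 | 10.8%, about 21 of 193 |
| Highest at both times, each way | 2.0% | 8.6% |

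A simulation of 400,000 subjects agrees within its error (3.9% vs 0.8%, and 14.2% vs 3.5%). With higher agreement between tracings (p = 5%, ρ = 0.8) the SAP rule gives 1.8% vs 0.4%, a net of about 3 of 193.

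**If one interpretation is recorded per set.** There is then one value per ordinary visit, so P(abnormal) = q under either rule and the net is 0. Only days with a repeat or extra set can contribute.

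**If Baseline times tie or are missing.** The Baseline value becomes the mildest of three. The same range then gives 5.7% to 19.0% against 0.1% to 0.2%. Nothing in the documents suggests that times will be shared or missing, so this is not the main case.

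**Overall-worst table.** The visit side is the worst of all readings by design, so only the Baseline choice is open. With full attendance there are 8 × 3 = 24 post-baseline tracings. Among Baseline-normal subjects the shift to abnormal is 1 − M(25)/M(1) = 9.7% to 41.3% with last-of-three at Baseline, and 1 − M(27)/M(3) = 6.9% to 34.4% with worst-of-three. Most of it remains under a symmetric rule.

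**The case against.** **The triplicate may already be a single unit.** The closing sentence of 5.3.4 treats it as one assessment, and the denominators in 14.4 refer to a subject's interpretation in the singular. Central evaluation of every tracing does not prove three separate verdicts. On that reading, routine triplicates never reach the same-day rule. This stands as a possible reading and is why the size cannot be fixed. It does not close the gap, because the sentence makes the triplicate one assessment by averaging, which is undefined for normal/abnormal.

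**The rule errs towards reporting harm, and nothing is tested.** Both are true: no error rate is affected and all results are listed. But the SAP gives no safety rationale, 5.3.4 covers categorical efficacy data as well, and an inflated rate of emergent abnormality can hide a real effect as easily as imitate one.

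**Baseline is screened.** Subjects with a clinically significant abnormal Baseline ECG are excluded (Protocol 4.2, criterion 9), so equal abnormal rates at Baseline and visits are an idealisation. This stands: some excess of normal-to-abnormal shifts may remain under any rule.

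**Stronger readings that the documents do not support.** A reader might infer that the shift table will necessarily show false worsening; that requires several same-day interpretations that disagree. A reader might infer that the QT findings are affected; QTcF values, changes, categories and potentially clinically important criteria are numeric and rest on the triplicate average. A reader might extend the point to CGI; it is scheduled once per visit and no CGI shift table is planned.

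**Conclusion.** The point holds as a conditional one. The asymmetry is explicit in SAP 5.3.4, it feeds the by-visit ECG shift table in 14.4, and any net effect of it can only be towards apparent worsening. It acts on every triplicate if interpretations are recorded per tracing, and only on repeat or extra sets if they are recorded once per triplicate.

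The size cannot be derived from the documents. Under the assumed rates and correlations, per-tracing interpretation and timed Baseline tracings, the net excess is about 3 to 11 percentage points of subjects at a visit. It is near zero with one interpretation per set. QTcF and CGI summaries are not shown to be affected, and in the overall-worst table only the Baseline choice is in question. This is a cheap improvement to the plan, not a flaw that undermines the primary safety analysis.

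**What to change.** 1. In SAP 5.3.4, use the same same-day selection rule for categorical data at Baseline and after Baseline, whether or not times are recorded.
2. In SAP 14.4, state whether the cardiologist's interpretation is recorded per tracing or per set. If per tracing, reduce each triplicate to one normal/abnormal result in the same way at every visit including Baseline, before either shift table is built. One option is to call the set abnormal if any tracing in it is abnormal.

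The cost is a few sentences and a small programming change, with no new data. A worst-of-set rule has a real downside: more subjects count as abnormal at Baseline, so fewer can show a new abnormality. In the range above, Baseline-abnormal rises from 5.0% to 8.1% (p = 5%, ρ = 0.6), or from 10.0% to 20.8% (p = 10%, ρ = 0.3). Any rule applied identically at both times, such as last tracing at both, also removes the imbalance caused by selection. None removes regression due to Baseline ECG eligibility screening, and the report should say so.

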5.4 Missing Data

In general, missing data will not be imputed unless otherwise specified in this document.

5.4.1 Missing or Incomplete Date for Last Dose of Study Drug

The missing last dose date of study drug for a subject who completed or early terminated from the study will be imputed using the last expected dosing date, which is defined as the minimum

of the non-missing drug return date of the last dispensed drug kits, the last drug dispensed date plus the number of days that the dosing would continue per protocol or the end-of-treatment/early termination visit (EOT/ET) date, whichever occurs earlier. For the incomplete last dose date of the study drug, the imputation will be compared against the last expected dosing date defined as above. Details will be provided in a separate specifications document. The missing or incomplete dates will be displayed in the data listings as reported on the eCRF rather than the imputed dates.

For data summarization before final database lock, if a subject is still ongoing at the time of analysis, then this subject's last dose date will be imputed using the database extract date.

5.4.2 Missing or Incomplete Dates for Prior or Concomitant Medications

Missing or incomplete medication start or end dates will be imputed for the purpose of determining whether the medications are taken concomitantly (see [Section 11](#) for definition). When the chronological order of medication use relative to the study drug treatment period is unclear due to missing or incomplete date(s), the medication will be considered as concomitant. The imputation algorithms will be provided in a separate specifications document. The missing or incomplete dates will be displayed in the data listings as reported on the eCRF rather than the imputed dates.

5.4.3 Missing or Incomplete Dates for Adverse Events

Missing or incomplete adverse event (AE) start dates will be imputed for the purpose of determining whether the AEs are treatment-emergent (see [Section 14.1](#) for definition). When the chronological order of an AE onset relative to the study drug treatment period is unclear due to missing or incomplete date(s), the AE will be considered as treatment-emergent. The imputation algorithms will be provided in a separate specifications document. The missing or incomplete dates will be displayed in the data listings as reported on the eCRF rather than the imputed dates.

5.4.4 Missing Severity Assessment for Adverse Events

If the severity is missing for an AE starting on or after the date of the first dose of study drug, then a severity of "Severe" will be assigned. The imputed values for severity assessment will be used for incidence summaries, and the actual values will be presented in data listings.

5.4.5 Missing Relationship to Study Drug for Adverse Events

If the relationship to study drug is missing for an AE starting on or after the date of the first dose of study drug, a causality of "Related" will be assigned. The imputed values for relationship to study drug will be used for incidence summaries, and the actual values will be presented in data listings.

5.5 Character Values of Clinical Laboratory Variables

If the reported value of a clinical laboratory variable cannot be used in a statistical analysis due to, for example, a character string reported for a numeric variable, an appropriately determined coded value will be used in the statistical analysis. The coding algorithms will be provided in a separate specifications document. The actual values as reported in the database will be presented in data listings.

6 SUBJECT DISPOSITION

The number of sites that enrolled at least one subject and number of subjects enrolled will be summarized by region (United States [US] and rest of world) and overall. Enrolled subjects are defined as those subjects who have informed consent for study -070 and are not recorded as a rollover failure.

For enrolled subjects, the number and percentage of subjects in the Safety Analysis Set will be summarized. A listing will be provided displaying all subjects excluded from the Safety Analysis Set (if any), and will include reason(s) for exclusion.

The number and percentage of subjects who completed the study or discontinued (all discontinued and by primary discontinuation reason including the reason due to COVID-19) will also be summarized. Summaries by region will also be presented. A listing will be provided on the reasons for premature study drug/study discontinuation.

7 PROTOCOL DEVIATIONS

Protocol deviations will be reviewed regularly over the course of the study. The review process, definition of the deviation categories, and the classification of a deviation as major or minor are detailed in the Protocol Deviation Management Plan. Protocol deviations will also be assessed with respect to relationship to COVID-19.

A summary of the number and percentage of subjects with major protocol deviations for each deviation category will be presented in three ways: all protocol deviations, COVID-19 related protocol deviations, and non COVID-19 related protocol deviations.

Two listings of protocol deviations will be provided: all deviations and COVID-19 related protocol deviations.

8 DEMOGRAPHICS AND OTHER BASELINE CHARACTERISTICS

8.1 Demographics and Other Baseline Characteristics

Demographics and open-label Baseline characteristics will be summarized for the Safety Analysis Set using descriptive statistics. Variables include age, age category (5-12 years and 13-

17 years), sex, primary race (subjects of multi-racial background can only identify/select one primary race on eCRF, or choose “other” and specify), ethnicity, height, weight, body mass index (BMI), intelligence quotient (IQ), IQ categories (<70 and \geq 70), region, and caregiver relationship.

The reported age reflects a subject’s age at the open-label Baseline visit date. Age will be presented both as continuous and categorical (5 through 12 years old or 13 through 17 years old). If there are discrepancies in the values between the IRT system and the clinical database, categories based on the IRT system and clinical database will each be presented separately.

8.2 Baseline Disease Characteristics

Disease characteristics at Baseline will be summarized for the Safety Analysis Set using descriptive statistics. Baseline ABC subscale scores, CGI-S of irritability score, RBS-R score, VABS-Socialization score, CGSQ score, and ESRS-A score will be presented as continuous variables. CGI-S of irritability score will also be presented as categorical variables using discrete categories.

9 MEDICAL HISTORY

Medical and surgical history data will be coded using Medical Dictionary for Regulatory activities (MedDRA) version 24.0 or higher. The subject incidence will be summarized for each system organ class (SOC) and preferred term by cohort and overall, for Safety Analysis Set. A subject will be counted only once per SOC or per preferred term for the summary.

A listing of the SOC, preferred term, body system, verbatim term for the medical history condition/event, start and stop dates (when available), and an indicator for whether or not the condition is ongoing will be provided.

10 EXTENT OF EXPOSURE AND TREATMENT COMPLIANCE

Summaries of exposure and compliance to study drug will be provided for the Safety Analysis Set.

10.1 Exposure to Study Drug

The pimavanserin dose levels are expressed as free base.

10.1.1 Exposure to Open-label Pimavanserin

For each subject, the duration of exposure to open-label pimavanserin (open-label last dose date – open-label first dose date + 1), cumulative dose (first multiply the number of doses taken by the dose level for each kit utilized during the open-label study period, then sum the results from

all kits), and average daily dose (cumulative dose in mg divided by duration of open-label exposure in days) will be calculated and summarized.

Duration of OL pimavanserin exposure will be summarized as both continuous and categorical variables. For categorical presentation, the number and percentage of subjects in each of the following categories will be presented: <2 weeks (1 to 13 days), 2 to <6 weeks (14 to 41 days), 6 to <12 weeks (42 to 83 days), 12 to <20 weeks (84 to 139 days), 20 to <28 weeks (140 to 195 days), 28 to <36 weeks (196 to 251 days), 36 to <44 weeks (252 to 307 days), 44 to <52 weeks (308 to 363 days), and \geq 52 weeks (364 days or longer). Kaplan-Meier curves of duration on study drug will also be presented. In addition, summaries of whether subjects had any dose change (yes vs. no), their highest dose level (20 mg or 34 mg), their lowest dose level (10 mg or 20 mg), and their last dose level (10 mg, 20 mg, or 34 mg) will also be provided.

